1.2 SCHEMATIC OF STUDY DESIGN

An overview of the study design is provided in [Figure 1](#).

Figure 1 Overview of Study Design

1.3 SCHEDULE OF ACTIVITIES

The schedule of activities (SoA) for the mass balance (MB) cohort is provided in [Table 1](#) and [Table 2](#). The SoAs for the absolute bioavailability (BA) cohort is provided in [Table 3](#) and [Table 4](#).

Table 1 Mass Balance Cohort – Main Table

Assessments	Screening	Treatment Period				Follow Up Call	Early termination or Unscheduled visit
	Day -28 to Day -2	Day -1	Day 1	Day 2	Day 3 to Day of Discharge	Day 29±3	
Time Relative (h)			0	24			
Assessments							
Informed Consent	X						
Eligibility	X	X					
Demography	X						
Vein assessment for venipunctures/cannulation	X						
Medical History	X	X					
Physical Examination ^a	X	X			X ^j		X
Vital Signs ^b	X	X	X		X ^j		X
ECG-12 lead ^c	X	X	X		X ^j		X
Hematology ^d	X	X			X ^j		X
Blood Chemistry ^d	X	X			X ^j		X
Coagulation ^d	X	X			X ^j		X
Urinalysis ^d	X	X			X ^j		X
Viral Serology ^e	X						
SARS-CoV-2 ^f	X	X			X		X
Lipids ^d	X	X			X ^j		X
Drug/Alcohol Test	X	X					
Oral Administration of [¹⁴ C] RO7049389 suspension			X				
IV Administration of [¹³ C] RO7049389 solution			X				
Blood sampling for PK, radioactivity counting and metabolic profiling ^g			X	X	X		X ^l
Urine sampling for PK, radioactivity counting and metabolic profiling ^g			X	X	X		
Feces sampling for radioactivity counting and metabolic profiling ^g		X ^k	X	X	X		
Clinical Genotyping ^h			X				
In-Clinic Stay		X	X	X	X		
Discharge ⁱ					X		
Adverse Events					X		
Previous and Concomitant Treatments					X		

Table 1 Mass Balance Cohort – Main Table (cont.)

- a) A full physical examination is required at screening and day of discharge. At other visits (or as clinically indicated), limited, symptom-directed physical examinations should be performed at the discretion of the Investigator. Body weight will be recorded each time. Height and BMI will only be done at screening.
- b) Vital signs include triplicate measurements of blood pressure and heart rate (taken approximately 1 minute apart) and a single assessment of body temperature (oral). Blood pressure and heart rate measurements will be assessed in a supine position after ≥ 5 minutes of rest.
- c) 12-lead ECGs will be obtained after the participant has been in a supine position for at least 10 minutes. Automated ECG intervals (PR [PQ], QRS, QT, QTcF, RR) and HR will be captured or calculated, and the changes in T-wave and U-wave morphology will be documented.
- d) Samples for clinical laboratory tests (hematology, chemistry, coagulation, urinalysis, and lipids) should be collected in the morning/at the most appropriate time. Creatinine clearance (CrCl) will be calculated using the Cockcroft-Gault formula at screening *and on Day -1*.
- e) Hepatitis A virus (HAV) IgM antibody, hepatitis B surface antigen (HBsAg), hepatitis C virus (HCV) RNA, total hepatitis D virus (HDV) antibody, hepatitis E virus (HEV) IgM antibody, human immunodeficiency virus (HIV-1 antibody and HIV-2 antibody, or HIV-1/2 antibody).
- f) Testing for SARS-CoV-2 may be performed based on current infection rates and availability of tests. If required, SARS-CoV-2 antibody will be done at screening. SARS-CoV-2 antigen will be done at screening, pre-admission, day before discharge *or* day of discharge.
- g) Radioactivity counting will be continued until discharge criteria are met.
- h) If the blood sample is not collected on Day 1, it may be collected at any time during the conduct of the clinical study.
- i) The participant will not be discharged until criteria are met. This is up to a maximum of 264 hours post-dose (Day 12) in-clinic stay, and could include a further 5 days collection of urine and feces samples at home, if required.
- j) Assessments done on the day of discharge. Tests should be performed after an overnight fast (for at least 10 hours).
- k) Only one sample is collected. It will be kept and processed only if the pre-dose sample on Day 1 cannot be obtained.
- l) Only collecting the PK sample.

Table 2 Mass Balance Cohort – Detailed Table

Period	Day	Scheduled Time (h)	Oral Administration of [¹⁴ C] RO7049389 suspension	IV Administration of [¹³ C] RO7049389 solution	Blood sampling for PK of [¹³ C] RO7049389 and its [¹² C] metabolites	Blood sampling for PK of [¹³ C] RO7049389 and [¹³ C] M5	Blood sampling for [¹⁴ C] drug related material radioactivity counting	Blood sampling for [¹⁴ C] drug related material metabolic profiling	Urine sampling for [¹⁴ C] drug related material radioactivity counting and metabolic profiling	Feces sampling for [¹⁴ C] drug related material radioactivity counting and metabolic profiling
Screening	Day -28 to Day -2									
	Day -1									^f
Period 1	Day 1	Pre-dose			X		X	X	X ^e	X
		0	X ^a							
		0.5			X		X			
		1			X		X	X		
		1.5			X		X			
		2	X ^b	X ^c	X ^c		X ^c	X ^c		
		2.1333			X ^d					
		3			X	X	X			
		4			X	X	X	X		
		6			X	X	X			
		8			X	X	X	X		
		10			X	X	X			
		12			X	X	X	X		
	Day 2	24			X	X	X	X	12-24 hr	
		36			X	X	X	X		24-48 hr
	Day 3	48			X	X	X	X		24-48 hr
	Day 4	72			X	X	X	X	48-72 hr	48-72 hr
	Day 5	96					X	X	72-96 hr	72-96 hr
	Day 6	120					X	X ^g	96-120 hr	96-120 hr
	Day 7	144					X	X ^g	120-144 hr	120-144 hr
	Day 8	168					X		144-168 hr	144-168 hr
	Day 9	192					X ^h		168-192 hr ^h	168-192 hr ^h
	Day 10	216					X ^h		192-216 hr ^h	192-216 hr ^h
	Day 11	240					X ^h		216-240 hr ^h	216-240 hr ^h
	Day 12	264					X ^h		240-264 hr ^{h,i}	240-264 hr ^{h,i}

Table 2 Mass Balance Cohort – Detailed Table (cont.)

- a) Participants will fast overnight for at least 10 hours prior to oral administration and fasted 4 hours post administration.
- b) Intravenous infusion administration over 10 minutes.
- c) Collected prior to start of infusion.
- d) Collected at the end of infusion.
- e) Spot urine sample.
- f) Only one sample is collected. It will be kept and processed only if the pre-dose sample on Day 1 cannot be obtained.
- g) Metabolic profiling analyses may not be done depending on the radioactivity level.
- h) Continued until discharge criteria are met.
- i) If on Day 12 the discharge criteria are not met, the participant will be discharged and, urine and feces samples will be collected by the subject at home in 24 hours intervals for up to 5 days or until the discharge criteria are met.

Table 3 Absolute BA Cohort – Main Table

Assessments	Screening		Treatment Period				Follow Up Call Period 2, Day 29±3	Early termination or Unscheduled visit
	Day -28 to Day -2	Day -1	Day 1	Day 2	Day 3	Day 4		
Time Relative (h)			0	24	48	72		
Assessments								
Informed Consent	X							
Eligibility	X	X						
Demography	X							
Medical History	X	X						
Vein assessment for venipunctures/cannulation	X							
Physical Examination ^a	X	X				X		X
Vital Signs ^b	X	X	X			X		X
ECG-12 lead ^c	X	X	X			X		X
Hematology ^d	X	X				X		X
Blood Chemistry ^d	X	X				X		X
Coagulation ^d	X	X				X		X
Urinalysis ^d	X	X				X		X
Viral Serology ^e	X							
SARS-CoV-2 ^f	X	X				X		X
Lipids ^d	X	X				X		X
Drug/Alcohol Test	X	X						
Pregnancy Test ^g	X	X						X
Follicle Stimulating Hormone ^h	X							
Oral Administration of [¹² C] RO7049389 tablet			X					
IV Administration of [¹³ C] RO7049389 solution			X					
Blood sampling for PK			X	X	X	X		X
Urine sampling for PK			X	X	X	X		
Clinical Genotyping ⁱ			X					
In-Clinic Stay		X	X	X	X			
Discharge ^j						X		
Adverse Events					X			
Previous and Concomitant Treatments					X			

RO7049389 —F. Hoffmann-La Roche Ltd

25/Protocol BP41811, Version 3

Table 3 Absolute BA Cohort – Main Table (cont.)

- a) A full physical examination is required at screening and day of discharge. At other visits (or as clinically indicated), limited, symptom-directed physical examinations should be performed at the discretion of the Investigator. Body weight will be recorded each time. Height and BMI will only be done at screening.
- b) Vital signs include triplicate measurements of blood pressure and heart rate (taken approximately 1 minute apart) and a single assessment of body temperature (oral). Blood pressure and heart rate measurements will be assessed in a supine position after \geq 5 minutes of rest.
- c) 12-lead ECGs will be obtained after the participant has been in a supine position for at least 10 minutes. Automated ECG intervals (PR [PQ], QRS, QT, QTcF, RR) and HR will be captured or calculated, and the changes in T-wave and U-wave morphology will be documented.
- d) Samples for clinical laboratory tests (hematology, chemistry, coagulation, urinalysis, and lipids) should be collected in the morning/at the most appropriate time. Creatinine clearance (CrCl) will be calculated using the Cockcroft-Gault formula at screening *and on Day -1*.
- e) Hepatitis A virus (HAV) IgM antibody, Hepatitis B surface antigen (HBsAg), Hepatitis C virus (HCV) RNA, total hepatitis D virus (HDV) antibody, hepatitis E virus (HEV) IgM antibody, human immunodeficiency virus (HIV-1 antibody and HIV-2 antibody, or HIV-1/2 antibody).
- f) Testing for SARS-CoV-2 may be performed based on current infection rates and availability of tests. If required, SARS-CoV-2 antibody will be done at screening. SARS-CoV-2 antigen will be done at screening, pre-admission, day before discharge *or* day of discharge.
- g) Serum beta-human chorionic gonadotropin (b-HCG) at screening, urine on all other occasions (females only). If urine test is positive, then a confirmatory serum test is needed.
- h) *Follicle stimulating hormone (females only to confirm post-menopausal status, performed at screening only).*
- i) If the blood sample is not collected on Day 1, it may be collected at any time during the conduct of the clinical study.
- j) Assessments will be performed after an overnight fast (for at least 10 hours).

Table 4 Absolute BA Cohort – Detailed Table

Period	Day	Scheduled Time (h)	Oral Administration of [¹² C] RO7049389 tablet	IV Administration of [¹³ C] RO7049389 solution	Blood sampling for PK of [¹² C] RO7049389 and its [¹² C] metabolites	Blood sampling for PK of [¹³ C] RO7049389 and [¹³ C] M5	Urine sampling for PK of [¹² C] RO7049389 and its [¹² C] metabolites
Screening	Day -28 to Day -2						
Period 1 and Period 2	Day -1	Pre-dose			X		X ^e
	Day 1	0	X ^a				
		0.5			X		
		1			X		
		1.5			X		
		2		X ^b	X ^c	X ^c	
		2.1333				X ^d	
		3			X	X	
		4			X	X	
		6			X	X	
		8			X	X	
	Day 2	10			X	X	8-12 hr
		12			X	X	
	Day 3	24			X	X	12-24 hr
		36			X	X	24-48 hr
	Day 4	48			X	X	
	Day 4	72			X	X	48-72 hr

- a) Participants will fast overnight for at least 10 hours prior to oral administration and fasted 4 hours post administration.
- b) Intravenous infusion administration over 10 minutes.
- c) Collected prior to start of infusion.
- d) Collected at the end of infusion.
- e) Spot urine sample.

2. INTRODUCTION

RO7049389 is an orally administered small molecule that is being developed for the treatment of chronic hepatitis B virus (HBV) infection.

2.1 STUDY RATIONALE

[REDACTED]

In order to better understand the disposition of RO7049389, it is important to characterize its metabolic profile and the rate and routes of elimination. To do this, it is necessary to administer a small amount of the drug, which has been radiolabeled in a stable position with carbon 14 [¹⁴C]. The intravenously (carbon 13 [¹³C]) will help differentiate non-absorbed drug and biliary secreted [¹³C] parent/metabolites in feces.

[REDACTED]

Therefore, in the absolute oral BA cohort of this study, RO7049389 will be administered orally (unlabeled) and intravenously [¹³C] to allow the quantification of absolute BA.

[REDACTED]

The results from the study will provide a more comprehensive understanding of the PK of RO7049389 and metabolites and allow for a more complete comparison of the routes of elimination and metabolic pattern of RO7049389 between animals and humans. The risks to the individual participant due to exposure to RO7049389, radiation, or study-related procedures are considered acceptable in this study.

[REDACTED]

the doses have been demonstrated to be safe and well tolerated in the Phase 1 study YP39364.

The rationale for the study design is provided in Section 4.2.

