3. OBJECTIVES AND ENDPOINTS

	Objectives	Endpoints
Primary	
 To characterize the mass balance (MB), routes, and rates of elimination of [¹⁴C] RO7049389. To determine the absolute oral bioavailability (BA) of RO7049389. 	
 Percentage of dose excreted in urine. Percentage of dose excreted in feces. Absolute oral BA for RO7049389.
Secondary		
 •
	
 To determine the plasma concentration of RO7049389, its identified three metabolites (RO7121986, RO7255420, and RO7255422), total drug-related radioactivity and related pharmacokinetic (PK) parameters. 	
 C_{max}, AUC_{last}, AUC_{0-inf}, t_{max}, CL/F, CL, CL_r, Ae, V/F, and $t_{1/2}$ of RO7049389 and its identified three metabolites, and total drug-related radioactivity, if appropriate.
	
 To identify and quantify circulating and excreted metabolites of RO7049389 in plasma, urine, and fecal samples based on radioactive metabolic profiling. 	
 A metabolic profile for RO7049389 and metabolites, and their structural elucidation, if appropriate. C_{max}, AUC_{last}, AUC_{0-inf}, t_{max}, CL/F, CL_r, Ae, V/F and $t_{1/2}$ of other major metabolites related radioactivity, if appropriate.
	
 To evaluate the safety and tolerability of one or two single-doses of RO7049389 in healthy participants. 	
 Adverse events (AEs), clinical laboratory values, vital signs, electrocardiogram (ECG), and physical examination.

OBJECTIVES AND ENDPOINT (CONT.)

Exploratory		
	
• To determine whether genes relating to drug-metabolizing enzymes and/or drug transporters affect the PK and/or the safety profile of RO7049389.	
• The pharmacogenetics of metabolizing enzymes (CYP3A4, UGT1A3) and transporters (OATP1B) possibly involved in the absorption, distribution, metabolism, and excretion of RO7049389 and its major metabolites.
	
• To determine the relative BA of RO7121986.	
• C_{max}, AUC_{last}, $AUC_{0-\infty}$ of RO7121986 after oral and intravenous (IV) administration of RO7049389.

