4.2 SCIENTIFIC RATIONALE FOR STUDY DESIGN

The study rationale is provided in Section 2.1.

The primary objectives of this study are to characterize the routes and rates of elimination of [¹⁴C]-labeled RO7049389 and to assess the absolute oral BA of a single-dose of 600 mg and 1000 mg of RO7049389. Drug concentrations or radioactivity in plasma, urine, and feces is assumed to be objective measurements, which cannot be affected by volunteer or staff behavior. Therefore, it is generally accepted to conduct MB study and absolute BA study with an open-label design, without placebo treatments, and since the evaluation of safety and tolerability is not a primary objective of this study, an open-label design was deemed appropriate.

For the absolute BA cohort, to minimize the number of participants needed and reduce inter-subject variability, this study will follow a two-period design instead of a parallel design. The duration of the washout period was established based on the known PK profile of RO7049389.

The concept of simultaneous dosing with a labeled IV dose and an unlabeled oral dose to determine absolute oral BA is well-established using stable non-radioactive isotope such as ¹³C. This technique allows the fate of the IV dose to be distinguished from the

oral dose by means of the isotopic tracer. Plasma concentrations will be determined by LC-MS/MS and the [¹³C]-labeled drug administered intravenously will be distinguished from the [¹²C]-unlabeled drug (i.e., in this study RO7049389) administered orally by virtue of their different molecular masses, using mass spectrometry detection. Dose-normalized AUCs of [¹²C]-unlabeled drug on the one hand and [¹³C]-labeled drug on the other hand will be compared to determine absolute oral BA. The principle advantage of the isotopic method is that the plasma drug concentration relating to the IV and oral doses will be measured in the same plasma sample, thereby eliminating inter-occasional variability and, in theory, eliminating any concentration-dependent clearance.

In this study, 100 µg of [¹³C] RO7049389, the IV tracer, will be administered 2 hours (the estimated t_{max} of the oral dose) after the oral dose of RO7049389 as a 10-minute infusion. Administering IV dose at the t_{max} of the oral dose is expected to reduce errors in BA estimation due to concentration dependent clearance considering the observed non-linear PK of RO7049389 in the Phase 1 studies.

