8.5 PHARMACOKINETICS

Mandatory blood and urine samples to evaluate concentrations of study treatment (RO7049389) and its metabolites (RO7121986, RO7255420, and/or RO7255422) will be collected. Mandatory blood, urine, and feces samples to measure the radioactivity and metabolic profiling will be also collected. The date and time of each sample collection will be recorded in the eCRF. The PK samples will be taken as outlined in the SoAs (Section [1.3](#)).

A PK sample will also be collected following occurrence of a dose-limiting event or SAE.

- Total radioactivity will be measured in plasma, whole blood, urine, and feces samples from MB cohort by liquid scintillation counting (LSC, Pharmaron, Hoddesdon EN11 9FH UK). Samples with low levels of radioactivity that cannot be quantified by LSC may be analyzed using AMS, if necessary.

- Metabolic profiling will be conducted in plasma, urine, and feces and blood pellet (if appropriate). The metabolic profiling samples may not be assessed if there are insignificant levels of [¹⁴C]-radioactivity present. The best approach for the pooling strategy of metabolic profiling samples (e.g., urine, feces, plasma, and blood pellet) must be agreed upon between the clinical study site and the Sponsor prior to being performed. The results of the metabolic profiling analysis may be reported separately from the main clinical study report.
- Concentrations of [¹²C] RO7049389, [¹²C] RO7121986, [¹²C] RO7255420 and [¹²C]-RO7255422 in plasma samples from both MB cohort and absolute BA cohort will be measured using a validated liquid chromatography–mass spectrometry (LC-MS/MS) method by Q2 solution (Ithaca, NY 14850 USA).
- Concentrations of [¹³C] RO7049389 and [¹³C] RO7121986 in plasma samples from both MB cohort and absolute BA cohort will be measured using a validated LC-MS/MS method by Q2 solution (Ithaca, NY 14850 USA).
- Concentrations of [¹²C] RO7049389, [¹²C] RO7121986, [¹²C] RO7255420 and [¹²C] RO7255422 in urine samples from absolute BA cohort will be measured using a validated LC-MS/MS method by Q2 solution (Ithaca, NY 14850 USA).
- Concentrations of RO7049389 other new identified metabolite(s) from absolute BA cohort as appropriate in plasma and urine samples may be measured using a validated LC-MS/MS method by Q2 solution (Ithaca, NY 14850 USA).

If required, remaining PK samples may also be used for assay development/validation experiments.

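### Does the rationale's claim about telling unabsorbed from biliary drug in feces require a fecal [13C] assay or a pre-specified split?

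*Combined protocol and SAP*

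**What the plan says.** The rationale, in Section 2.1 and repeated in the synopsis (Section 1.1), says that the intravenous [13C] dose "will help differentiate non-absorbed drug and biliary secreted" [13C] parent and metabolites in feces. The sentence lacks a noun, and blacked-out text stands close to it.

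The measurements are set out elsewhere:

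- **[13C].** Section 8.5 states that [13C] RO7049389 and [13C] "RO7121986 in plasma samples from both MB cohort and absolute BA cohort will be measured using a validated LC-MS/MS method". No other matrix is named for this label.
- **Feces.** These are collected in the mass balance cohort only. Section 8.5: "Total radioactivity will be measured in plasma, whole blood, urine, and feces samples from MB cohort". The feces column of Table 2 (Section 1.3) is for [14C] "drug related material radioactivity counting and metabolic profiling", and Section 3 frames the metabolite objective as work "in plasma, urine, and fecal samples based on radioactive metabolic profiling".
- **Pooling.** "The best approach for the pooling strategy of metabolic profiling samples" is left by Section 8.5 to agreement between site and sponsor before the work is done.
- **Analysis.** Section 9.3.3 lists F, and clearance and steady-state volume after intravenous dosing, among the plasma parameters. It presents all parameters as individual listings as well as summaries. Its only fecal parameter is recovery of total [14C]. Mass balance data are read descriptively. Further parameters may be added, and population and physiologically based PK modelling may be done and reported separately.

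**The concern.** The sentence names a label, the analytes and a matrix, so a reader may expect a [13C] result in feces. None is planned. The [14C] label is given by mouth only, so total fecal [14C] adds together drug that was never absorbed and drug that was absorbed and later secreted. Total recovery alone cannot separate them.

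Routes of elimination belong to a primary objective. If fecal recovery turned out to be high, its meaning would depend on this split: poor absorption and extensive biliary secretion give the same total. Section 9.3.3 does not say how plasma [13C] data would be combined with fecal [14C] data, so the reading might be made after the fact, with no stated bound or assumptions.

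**Working it through.** **Labels against matrices (Sections 1.3, 8.5 and 9.3.3)**

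| Label | Route | Plasma | Urine | Feces |
|---|---|---|---|---|
| [12C] | oral | both cohorts | bioavailability cohort | not planned |
| [13C] | intravenous | both cohorts | not planned | not planned |
| [14C] | oral | mass balance | mass balance | mass balance |

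The mismatch is confirmed. The next question is whether the intravenous dose still helps.

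**What plasma [13C] contributes.** Let fa be the fraction of the oral dose absorbed. F = fa × (fraction escaping first pass), so F ≤ fa and the unabsorbed share satisfies 1 − fa ≤ 1 − F. The unabsorbed share found in feces also cannot exceed fecal [14C] recovery R. Therefore

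U1 = min(R, 1 − F), and the absorbed-then-secreted share lies between R − U1 and R.

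If unabsorbed drug also leaves the gut unchanged, it cannot exceed the fecal [14C] parent P, so U2 = min(P, 1 − F).

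The documents give no F, R or P. The values below are assumptions, with R = 0.70 and P = 0.25.

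| F | U1 | Secreted share from U1 | U2 | Secreted share from U2 |
|---|---|---|---|---|
| 0.3 | min(0.70, 0.70) = 0.70 | 0 to 0.70 | 0.25 | 0.45 to 0.70 |
| 0.5 | min(0.70, 0.50) = 0.50 | 0.20 to 0.70 | 0.25 | 0.45 to 0.70 |
| 0.8 | min(0.70, 0.20) = 0.20 | 0.50 to 0.70 | 0.20 | 0.50 to 0.70 |

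So the intravenous dose does bear on the question. It helps much at high F and little at low F. At F = 0.3 the bound on its own excludes nothing.

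**How firm the bound is.** Section 4.2 times the infusion at the oral peak to reduce "errors in BA estimation due to concentration dependent clearance considering the observed non-linear PK of RO7049389". If a relative error of 20% in F remained (assumed), 1 − F would run from 1 − 0.36 = 0.64 to 1 − 0.24 = 0.76 at F = 0.3, from 0.40 to 0.60 at F = 0.5, and from 1 − 0.96 = 0.04 to 1 − 0.64 = 0.36 at F = 0.8. The bound is approximate, and in relative terms least firm at high F, where it is most useful.

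**Would a fecal [13C] assay settle it?** Take fa = 1, a first-pass biliary loss of 0.5, and 60% of systemic drug secreted into feces (all assumed). Then F = 0.5 and the true secreted share is 0.5 + 0.5 × 0.6 = 0.80. With nothing unabsorbed, R = 0.80. Fecal [13C] would be 0.6 of the intravenous dose, and F × 0.6 = 0.30, far below 0.80, because the intravenous label never undergoes oral first pass. The unabsorbed share would then be bounded by 0.80 − 0.30 = 0.50, which equals 1 − F. In this example the assay adds nothing to what plasma already gives. The oral dose is also 600 mg / 100 µg = 6000 times the intravenous dose, so selectivity in feces would have to be shown first.

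**The case for a change.** The strongest case for a change is that it is cheap: reword one repeated sentence and add two derived quantities for six participants, from data already planned. With R = 0.70, F = 0.3 and P = 0.25, stating U2 as well as U1 lowers the cap on the unabsorbed share from 0.70 to 0.25. Profiling results may also be reported apart from the main study report, so the link between F and the fecal data could be lost. The bioanalysis and analysis sections, where a fecal [13C] assay or a method for the split would appear, show no redaction on this point.

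Part of this stands. The sentence is looser than the measurements behind it, and the visible text does not describe the indirect route.

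The rest does not carry a change. The rationale says only that the dose will help, and it does. U1 is one subtraction and one comparison from quantities that Section 9.3.3 already lists. U2 depends on no degradation in the gut lumen, and its gain in the example comes from the chosen P; at F = 0.8 it adds nothing unless P is below 0.20. Calculating U2 per participant would require at least 6 fecal pools instead of possibly 1, which is extra profiling work on a matter the protocol deliberately leaves to later agreement. Nor is there a hypothesis test or decision rule in the mass balance cohort that reading the data afterwards could bias.

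**Conclusion.** No change to the plan follows. The rationale sentence points to a fecal [13C] result that the visible protocol does not plan, but this is imprecise wording and a gap that analysts fill sensibly. Followed as written, the plan still yields the urinary percentage of dose, the fecal percentage of dose and F. None of these changes by any amount if the bound is pre-specified, and no endpoint promises the split. Correcting the sentence would be editorial.

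This rests on three points. F is read as available for each mass balance participant: Section 9.3.3 lists it without limiting it to a cohort, and Section 8.5 assays both [12C] and [13C] in that cohort's plasma. The illustrative sizes rest on assumed F, R and P, since the documents give none. The redacted text near the sentence may hold further reasoning, so its absence from the visible pages is not held against the plan.
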